**A Mechanistic Perspective on Post-Activation Performance
Enhancement Responsiveness: A Randomized Controlled
Study of Acute Changes in Muscle Architecture, Contractile
Property Kinetics, and Muscle Excitability**

NCT06982937

18.05.2025

Objectives and endpoints.

The primary objective is to test whether a heavy conditioning activity (CA; one set of 2–3 repetitions at ~90% 1RM) produces post-activation performance enhancement (PAPE) in countermovement jump (CMJ) height compared with a control treadmill warm-up within the 4–12 min window after the intervention. The analysis does not assume *a priori* when the maximal effect occurs; instead, the minute of maximal between-group difference (denoted T^*) will be identified empirically. The primary endpoint is the change in CMJ height from baseline (ΔCMJ) at post-intervention time points (4, 6, 8, 10, 12 min). Secondary endpoints include the time-course of ΔCMJ within the experimental group (EXP), individual responder status at each time point, and the associations between neuromuscular phenotype—estimated as %MHC-I from tensiomyography (TMG)—and the magnitude, timing, and likelihood of response. Ultrasound (USG) morphology (muscle thickness, pennation angle, derived fascicle length) will be analysed in parallel to performance endpoints. Electromyography (EMG), where available, will be treated analogously to USG/TMG (see below).

Data handling and derived variables.

At each time point, CMJ height is the mean of three trials; ΔCMJ and percentage change (% ΔCMJ) will be computed relative to baseline. Individual response is classified using MDC. USG outcomes will be averaged across three images; fascicle length is calculated as thickness divided by the sine of pennation angle (degrees converted to radians). TMG-based %MHC-I is estimated from delay, contraction, and half-relaxation times using the published multivariable model; TMG amplitudes and time constants may also be expressed as Δ or % Δ . If EMG is collected, signals will be band-pass filtered, rectified, quantified with 50-ms RMS, normalized (to MVC or M-wave), and summarized over task-relevant phases; % Δ at 4–12 min is computed analogously. Values >3.5 SD from group-time means will be flagged; primary analyses include all data, with winsorized sensitivity checks reported only if inferences change. Missing data will be not imputed for the primary analysis; mixed-effects models accommodate missingness assuming MAR.

Primary analysis and identification of the peak time (T^*).

The confirmatory analysis uses a RM-ANOVA with ΔCMJ as the outcome, Group (EXP vs CON), Time (time effect: 4, 6, 8, 10, 12 min), and Group \times Time. If the interaction is significant, we estimate adjusted between-group contrasts at each minute with Bonferroni correction across the five time points. T^* is defined as the minute showing the largest positive EXP–CON difference in estimated marginal means (EMMs) with the smallest p-value. We report the EMM difference at T^* (95% CI) and effect size (d’Cohen). Greenhouse–Geisser correction if needed.

Within-group time-course and kinetics.

To describe the temporal profile without prespecifying a target minute, we analyse ΔCMJ across time within EXP using a one-way repeated-measures ANOVA (or LMM if assumptions are violated), followed by Bonferroni-adjusted pairwise EMMs to locate the within-group peak. To characterise response timing at the individual level, we model time to first and time to peak response (4–12 min) using Kaplan–Meier curves with censoring at 12 min, compare strata by log-rank tests, and fit Cox proportional-hazards models to estimate hazard ratios (HR, 95% CI) and concordance (C-index). This kinetics framework provides an assumption-light estimate of when athletes typically express PAPE.

Responder analyses and discrimination.

Responder distributions (Positive/neutral/adverse) will be compared between EXP and CON at each minute using likelihood χ^2 test. For mechanistic discrimination at specific minutes (including T^* once identified), we fit logistic models with %MHC-I as a continuous predictor and report ORs (95% CI),

Nagelkerke R², AIC, Hosmer–Lemeshow calibration, and ROC-AUC with sensitivity, specificity, and Youden's J cut-offs. Moderation analysis also will be used with simple slope analysis.

Phenotype and morphology linkages (USG/TMG/EMG).

Associations between %MHC-I and Δ CMJ will be quantified at each minute using Pearson's r. USG variables (thickness, pennation angle, fascicle length) will be analysed with the same three lenses applied to performance: (i) within-EXP time-course (rmANOVA/LMM with Tukey), (ii) responder linkage at each minute (one-way ANOVA or robust alternative; Hedges' g for P vs X), and (iii) phenotype linkage (correlations and moderation models). TMG (e.g., Dm, Tc, Tr) and EMG (e.g., normalized RMS, median frequency) follow this identical framework to ensure coherence across modalities.

Moderation and mediation (pre-specified).

All moderators and predictors will be mean-centered; multicollinearity is checked (VIF < 5). Primary moderation models test whether (a) baseline CMJ modifies the effect of %MHC-I on Δ CMJ and (b) baseline morphology (thickness, pennation angle, fascicle length) modifies the effect of baseline CMJ on Δ CMJ. Significant interactions will be decomposed with simple slopes at -1 SD, mean, and +1 SD, with 95% CIs via nonparametric bootstrap (1,000 resamples) and publication-ready interaction plots. Exploratory mediation tests whether acute morphological change (e.g., % Δ thickness at a given minute) transmits baseline morphology effects to % Δ CMJ; indirect, direct, and total effects will be estimated by bootstrap (5,000 resamples; bias-corrected CIs) and interpreted cautiously.

Assumptions, multiplicity, and robustness.

Model diagnostics include residual normality (Shapiro–Wilk), homoscedasticity (residual–fitted patterns, Breusch–Pagan), linearity, and independence by design. Sphericity is tested for rmANOVA (Mauchly) with Greenhouse–Geisser corrections as needed. If mechanistic variables are skewed, appropriate transformations (e.g., log for EMG amplitude) are considered; otherwise we rely on LMM robustness. Multiplicity is controlled via Holm across the five between-group contrasts, FDR for correlation families, and restraint in post-hoc testing; moderation/mediation will be estimation-focused with full interval reporting and are not used to redefine the primary inference.

Reporting, visualization, and software.

We report means \pm SD with 95% CIs; between-group effects as Hedges' g; within-subject effects as d_{nZ} ; ANOVA-style effects as η^2 ; logistic results as ORs with AUC; and survival results as HRs with concordance. Figures include EMM trajectories with 95% CIs, individual waterfall plots with MDC bands, ROC curves for %MHC-I, Kaplan–Meier curves for first/peak response, interaction plots for significant moderations, and path diagrams for supported mediations. Analyses will be performed in Jamovi 2.6 and STATISTICA 13.1.

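### MDC labels after a single bout can split athletes whose true gain is identical, and the planned analyses give only indirect evidence that response differs between athletes

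*Combined protocol and SAP*

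**What the plan says.** The title concerns responsiveness, and 'Objectives and endpoints' lists "individual responder status at each time point" among the secondary endpoints. The intervention is a "heavy conditioning activity (CA; one set of 2–3 repetitions at ~90% 1RM"; no second session, crossover period or repeat exposure is described, and Group is a between-athlete factor in the primary analysis.

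'Data handling and derived variables' gives the measurement and the rule: "At each time point, CMJ height is the mean of three trials; ΔCMJ and percentage change (% ΔCMJ) will be computed relative to baseline", and "Individual response is classified using MDC". No MDC value, confidence level or reliability source is stated.

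Under 'Responder analyses and discrimination', the control arm enters through one comparison: "Responder distributions (Positive/neutral/adverse) will be compared between EXP and CON at each minute using likelihood χ^2 test". For phenotype, the same section says "we fit logistic models with %MHC-I as a continuous predictor and report ORs (95% CI"; neither a Group term nor the arms to be included are stated. It also mentions moderation analysis without listing terms.

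'Phenotype and morphology linkages' adds Pearson correlations of %MHC-I with continuous ΔCMJ and contrasts of morphology by responder category. The two models in 'Moderation and mediation' cross baseline CMJ with %MHC-I, and baseline morphology with baseline CMJ. Group is in neither interaction.

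**The concern.** A change larger than the MDC supports the statement that this athlete's score moved by more than error. It does not support the statement that this athlete's true response differs from another's. When the true gain is near the MDC, error alone decides who falls on which side, and the plan would report a mix of Positive and neutral athletes even if all had gained equally. The five post-intervention minutes do not solve this, because they follow the same bout and share one baseline measurement.

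Comparing label proportions between arms does not solve it either. Moving every EXP athlete up by the same amount changes those proportions. What would bear on the question is the spread of ΔCMJ in EXP set against the spread in CON, or a phenotype slope that differs between arms. Neither is planned. At stake is whether the study can speak about individual responsiveness, or only about a mean effect and the observed scores around it.

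**Working it through.** The plan states no sample size, SD, MDC value or expected responder rate, so there is no figure of its own to reproduce. The check asks what the labels do when true response is identical in everyone.

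**Assumptions (not in the documents).** Normal errors with the same SD in all athletes; MDC = z × SD of change error, with z = 1.96 for MDC95 and 1.645 for MDC90; two-sided alpha 0.05; sample sizes per arm as shown.

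**Labels at one minute.** For a uniform gain of k × MDC:

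- P(Positive) = Φ(z(k − 1))
- P(Adverse) = Φ(−z(k + 1))

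With z = 1.96 and k = 0.5, P(Positive) = Φ(−0.98) = 16.4% and P(Adverse) = Φ(−2.94) = 0.2%, leaving 83.5% neutral.

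| Uniform gain (× MDC) | Positive, MDC95 | Positive, MDC90 |
|---|---|---|
| 0 | 2.5% | 5.0% |
| 0.25 | 7.1% | 10.9% |
| 0.5 | 16.4% | 20.5% |
| 0.75 | 31.2% | 34.1% |
| 1.0 | 50% | 50% |
| 1.5 | 83.7% | 79.5% |
| 2.0 | 97.5% | 95.0% |

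True between-athlete variation is zero in every row. At 1.0 MDC an independent repeat would reproduce an athlete's label with probability 0.5² + 0.5² = 50%.

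**If the MDC does not match the trial's own error.** With actual error SD between 0.6 and 1.3 times the one the MDC assumes, the 0.5 MDC figure (MDC95) runs from 5% to 23%. The 1.0 MDC figure stays at 50%.

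**Across five minutes.** This was simulated with shared baseline error (change scores correlated 0.5), the same gain at every minute and MDC95. At least one Positive label occurs in 9% of athletes at zero gain, 42% at 0.5 MDC and 83% at 1.0 MDC. Positive at some minutes but not all: 41% at 0.5 MDC and 67% at 1.0 MDC, from error alone. This bears on the time-to-event analyses only if response there means crossing the MDC.

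**The planned chi-square under an identical benefit (simulated, MDC95).**

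| n per arm (assumed) | Rejects at 0.5 MDC | Rejects at 1.0 MDC |
|---|---|---|
| 10 | 15% | 84% |
| 20 | 38% | 98% |
| 40 | 63% | about 100% |

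These are correct rejections of equal distributions. They carry no information on whether athletes differ in response.

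**What the control arm can supply.** If ΔCMJ in EXP is the change that would have occurred under control plus the athlete's response, and the two are uncorrelated, then SD_EXP² − SD_CON² equals the variance of true response. It is zero in expectation under an identical gain, whatever share is labelled Positive.

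**Its precision.** At an assumed 15 per arm, a two-sided 5% test at one minute needs a variance ratio above F(0.975; 14, 14) = 2.98. If response SD equals the control-arm SD, so that the true ratio is 2, a one-sided 5% test has power 0.25, 0.43, 0.69 and 0.84 at 10, 20, 40 and 60 per arm. If response SD is half the control-arm SD, power is 0.09, 0.12, 0.17 and 0.21.

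**The case against.** The plan is not silent on whether response varies. The correlations and moderation models use continuous ΔCMJ and do not depend on labels, and a real association within EXP would be indirect evidence that change is not pure error. That stands. What these analyses cannot do without a Group term is separate differing response to the conditioning activity from variation also present after the treadmill warm-up. The Breusch–Pagan diagnostic might pick up unequal spread, but it does not estimate response variation.

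A reader might infer that random labels would lead the plan to a spurious phenotype. The documents do not support that. %MHC-I comes from TMG, a separate instrument from the jump test, so labels driven only by jump error would tend to give a null odds ratio and an AUC near 0.5, apart from ordinary false positives. A reader might also infer that a significant chi-square will be presented as proof of individual responsiveness. The plan says only that the distributions will be compared, which is a legitimate between-group comparison.

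The percentages depend on an MDC the plan does not state. If it came from single-trial error while each score averages three independent trials, 0.5 MDC would label Φ(−0.98 × √3) = 4.5% Positive. That stands as a limit on size, and the range above covers most of it.

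Finally, a variance comparison used as a pass/fail gate would be a poor remedy. The square root is undefined whenever SD_EXP falls below SD_CON, about half the time under no heterogeneity. At an assumed 15 per arm, a bootstrap gate at one minute would pass only about a quarter of the time even when response SD equals noise SD. This stands, and is why the fix asks for an estimate.

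**Conclusion.** The concern holds in a limited form. MDC labels can mix Positive and neutral athletes when the true gain is the same in all: 16%, 31% and 50% Positive at 0.5, 0.75 and 1.0 MDC under the MDC95 assumption. The mixture is substantial for gains of roughly 0.25 to 1.75 MDC and small well outside that range; the documents do not say where the expected gain lies. The chi-square cannot show that response differs between athletes, and the continuous phenotype analyses show it only indirectly.

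Two stronger readings go too far: that the labels are necessarily random, and that nothing planned bears on heterogeneity. That each athlete is exposed once is an inference from the single bout and between-athlete comparison described, since the text does not say so outright. Responder status is secondary and the confirmatory RM-ANOVA uses no labels, so this affects interpretation of the responder work and not the primary inference. It should be changed before analysis.

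**What to change.** Add to 'Responder analyses and discrimination':

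1. At each minute, and pooled over the five minutes in one model with group-specific between-athlete variance, report SD_EXP² − SD_CON² of ΔCMJ with a 95% CI that allows negative values. Give the signed square root as the SD of individual response. Treat it as an estimate, not a pass/fail gate.
2. Fit ΔCMJ on Group, %MHC-I and Group × %MHC-I in both arms, so that a phenotype association can be attributed to the conditioning activity.
3. Describe the MDC categories as observed change beyond MDC. Interpret the chi-square as a difference in proportions that a uniform shift can produce. Do not present logistic or ROC results as evidence of responder types unless item 1 or item 2 supports it.

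Stating the MDC's value, level and source alongside would let readers place the gain on the scale above.

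Cost: SAP wording, one variance estimate and one regression. No new data are needed, provided baseline TMG is collected in CON; the plan does not restrict it to EXP but does not say so explicitly. Downside: the variance estimate is imprecise in small groups and assumes that response to the conditioning activity is uncorrelated with the change seen under control, so the responder conclusion may be weaker.

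### The missing-data rule for the primary analysis relies on mixed models under MAR, but the confirmatory test is a classical RM-ANOVA that drops incomplete participants

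*Combined protocol and SAP*

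**What the plan says.** Under *Data handling and derived variables*, the rule for the primary analysis is: "Missing data will be not imputed for the primary analysis; mixed-effects models accommodate missingness assuming MAR".

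Under *Primary analysis and identification of the peak time*, the model is named: "The confirmatory analysis uses a RM-ANOVA with ΔCMJ as the outcome". Its factors are Group, Time (five post-intervention minutes) and their interaction, and it ends with "Greenhouse–Geisser correction if needed". Under *Assumptions, multiplicity, and robustness* the plan adds: "Sphericity is tested for rmANOVA (Mauchly) with Greenhouse–Geisser corrections as needed".

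A linear mixed model is named in three other places:

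- the ΔCMJ time-course within EXP, as "one-way repeated-measures ANOVA (or LMM if assumptions are violated";
- the USG time-course within EXP, with TMG and EMG following the same framework;
- the handling of skewed mechanistic variables.

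No section names a mixed model for the EXP–CON comparison, whether as main model, fallback or sensitivity analysis. On software the plan says: "Analyses will be performed in Jamovi 2.6 and STATISTICA 13.1".

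**The concern.** The missing-data rule describes a property of one model, while the confirmatory test is a different model. A classical RM-ANOVA needs a value at every time point. A participant with four of the five minutes contributes nothing, and the estimates are in general unbiased only if the incomplete participants are a random subset (MCAR). A likelihood-based mixed model uses every observed minute and is valid under the weaker MAR condition, which is the one the plan states.

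The difference matters if stopping depends on earlier jumps and differs between arms. The complete-case arm means are then biased, and so are the EXP–CON differences at each minute, including the one to be reported at T*. The sign depends on which arm loses participants. If weak jumpers leave EXP, the EXP–CON difference is inflated; if they leave CON, it is reduced.

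The text also leaves a choice open. An analyst who meets a missing jump could cite the data-handling section for a mixed model or the primary-analysis section for a complete-case ANOVA, after seeing the data.

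**Working it through.** **Which model is meant.** The words classical and complete-case do not appear in the plan; they are inferred. Mauchly's test and the Greenhouse–Geisser correction belong to the classical ANOVA, and a mixed model with a modelled covariance has no use for them. The plan also lists LMM separately, as an alternative to RM-ANOVA. Even for ΔCMJ within EXP, the switch to LMM is triggered by violated assumptions, not by missing values. The statement in the data-handling section that primary analyses use all data concerns values flagged beyond 3.5 SD, not absent ones.

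**Inputs.** The documents give the five minutes (4, 6, 8, 10, 12), but no sample size, SD, correlation or missingness rate. There is no plan figure to reproduce. Everything below is an illustration under assumptions, with ΔCMJ in SD units and a constant within-participant correlation r of 0.5 or 0.8.

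**1. Efficiency.** Suppose each minute is missing independently with probability m. The share of complete participants is (1−m)^5. For the likelihood model, the information is Σ over the 2^5 missingness patterns of P(pattern) × the inverse covariance of the observed minutes. The retained share is the full-data variance of a contrast divided by its variance from that information.

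| m | Complete rows | Likelihood, Group×Time (r=0.5 / 0.8) | Likelihood, single minute (r=0.5 / 0.8) |
|---|---|---|---|
| 1% | 0.99^5 = 95.1% | 98.8% / 98.8% | 99.4% / 99.8% |
| 5% | 0.95^5 = 77.4% | 94.0% / 93.8% | 96.9% / 98.7% |
| 10% | 0.90^5 = 59.0% | 88.1% / 87.7% | 93.6% / 97.3% |

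At the other extreme the same people miss all five minutes. Both methods then lose only 1%, 5% or 10%, and the mixed model recovers nothing.

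**2. Bias under MAR dropout in one arm.** A participant whose ΔCMJ is below −1 SD stops before the next minute with a fixed probability (1,000,000 simulated participants per row).

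| r | Stop probability | Arm incomplete | Complete-case bias of arm mean, range over minutes |
|---|---|---|---|
| 0.5 | 0.25 | 13.7% | +0.11 to +0.14 SD |
| 0.5 | 0.50 | 23.9% | +0.21 to +0.26 SD |
| 0.8 | 0.25 | 12.6% | +0.17 to +0.18 SD |
| 0.8 | 0.50 | 20.4% | +0.28 to +0.30 SD |

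The likelihood estimates are within 0.001 SD of the truth.

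With the stop probability tuned to leave 5% of the arm incomplete, the complete-case bias is +0.04 to +0.05 SD (r=0.5) or +0.06 to +0.07 SD (r=0.8).

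A check by hand: if the lowest 5% at minute 4 stop, the bias at minute 4 is φ(1.645)/0.95 = 0.109 SD. At later minutes it is r × 0.109, that is 0.054 SD (r=0.5) to 0.087 SD (r=0.8).

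A different mechanism gives a similar picture. With logistic dropout in EXP on the minute-4 value, loss of minutes 8 to 12 and r=0.7, the complete-case excess is about 0.05–0.07, 0.08–0.12 and 0.16–0.23 SD at 5%, 10% and 20% dropout. Likelihood estimates stay within about 0.002 SD of the full-data values.

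If both arms drop out alike and there is no effect, the contrast is unbiased.

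**3. False positives** (assumed n=20 per arm, 3,000 trials for each of the four rows above, no true effect). The Group×Time test with Greenhouse–Geisser rejects in 3.6–4.6% of trials, because the bias is nearly constant over minutes. The Group main effect rejects in 8.1–16.8%.

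**The case against.** The strongest reply is that the rule has two clauses joined by a semicolon. The second may describe only the mixed models the plan does name, in the secondary and mechanistic analyses. The plan would then be silent on incomplete participants in the RM-ANOVA rather than mistaken about them. This does not remove the problem. The sentence is about the primary analysis, and on the gentler reading the confirmatory test has no missing-data rule beyond not imputing.

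The points on size largely stand:

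- Nothing in the documents suggests substantial missingness, since all the primary outcomes fall within minutes 4–12.
- The larger bias figures need 13–24% of one arm, and none of the other, to stop because of poor jumps.
- At 5% one-arm incompleteness the bias is small against a single-minute standard error of √(2/20) ≈ 0.32 SD at 20 per arm. There the gain in root mean squared error from the mixed model is about 2% or less.
- The interaction gate is not inflated in these scenarios. The Group main effect is, but the plan does not use it as the gate.

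It is also fair that a detailed covariance specification goes beyond what is needed to remove the contradiction. The minimum remedy below would do that.

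**Conclusion.** The concern holds. As written, the plan attributes to its primary analysis a robustness to MAR missingness that its confirmatory RM-ANOVA does not have. The inference that the ANOVA is the classical form is well supported by the sphericity provisions and by the separate naming of LMM elsewhere.

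The practical effect depends on missingness that the documents do not describe. It is nil with complete data, a few hundredths of an SD with about 5% outcome-dependent loss in one arm, and up to about 0.3 SD in the heavier scenarios. The harm falls on the EXP–CON estimates and on efficiency, not on the error rate of the interaction gate. This should be fixed before analysis, but it does not undermine the design.

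**What to change.** **Preferred.** Make the confirmatory model a likelihood-based mixed model for ΔCMJ with Group, Time and Group×Time. It should use all observed minutes, an unstructured within-participant covariance and Kenward–Roger or Satterthwaite degrees of freedom. Prespecify a fallback for non-convergence that does not assume sphericity: heterogeneous Toeplitz first, heterogeneous autoregressive only as a last resort. The order matters. If the true correlation is constant, an autoregressive fit leaves +0.05 to +0.12 SD bias at minute 12, against +0.11 to +0.28 SD for complete cases; Toeplitz contains both structures. Keep the complete-case RM-ANOVA with Greenhouse–Geisser as a sensitivity analysis.

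**Minimum.** State that the RM-ANOVA is complete-case and rests on MCAR, report incomplete participants by arm and minute, and prespecify the mixed model as a sensitivity analysis.

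**Cost.** SAP wording, plus a check that the named software can fit the model; if it cannot, other software must be named. Design and data collection do not change. With complete data the minute means and EXP–CON differences equal those of the RM-ANOVA. The F tests can differ, because the covariance is no longer restricted to sphericity.

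### The confirmatory model for ΔCMJ omits baseline CMJ, so a chance baseline difference is only incompletely corrected; pre-specifying it as a covariate is a cheap improvement of uncertain size

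*Combined protocol and SAP*

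**What the plan says.** The section on the primary analysis and T* sets out the model: "The confirmatory analysis uses a RM-ANOVA with ΔCMJ as the outcome, Group (EXP vs CON", together with Time (five levels, from 4 to 12 min) and the Group × Time interaction. No baseline covariate is listed. If the interaction is significant, "we estimate adjusted between-group contrasts at each minute" follows, with Bonferroni correction over the five minutes.

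The endpoint is itself a change score (Objectives and endpoints): "The primary endpoint is the change in CMJ height from baseline (ΔCMJ) at post-intervention time points (4, 6, 8, 10, 12 min". Under Data handling and derived variables, "ΔCMJ and percentage change (% ΔCMJ) will be computed relative to baseline", so baseline CMJ exists for every participant who contributes a ΔCMJ.

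Baseline CMJ appears as a model term only under Moderation and mediation. Model (a) asks whether "baseline CMJ modifies the effect of %MHC-I on Δ CMJ". Model (b) asks whether baseline morphology "modifies the effect of baseline CMJ on Δ CMJ". The section on assumptions and multiplicity says that these models will not alter the primary inference, so they do not supply the missing adjustment. No baseline-adjusted sensitivity analysis of the primary endpoint is planned.

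**The concern.** The plan models baseline CMJ as a predictor of ΔCMJ in secondary work, leaves it out of the confirmatory model, and gives no reason. With equal SDs, baseline is negatively correlated with change whenever ρ is below 1. Two things follow. Variance in ΔCMJ that baseline could explain stays in the error term. And if the arms differ at baseline by chance, the arm that started higher tends to show the smaller ΔCMJ, whatever the conditioning activity does.

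At stake are the per-minute EXP–CON contrasts, the EMM difference at T* with its confidence interval, and the effect size. Timing matters too: a covariate added only after an imbalance has been seen would be a data-driven choice.

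**Working it through.** **Inputs.** The model terms, the endpoint and the five time points come from the document. It gives no sample size, power, alpha, sidedness, SD, allocation ratio or correlation, so there is no planned figure to reproduce. Assumed: parallel arms, 1:1 allocation, equal SD σ at baseline and post, ρ from 0.5 to 0.95, two-sided alpha 0.05.

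**1. Variance of one per-minute contrast.**
- Change score: proportional to 2σ²(1−ρ).
- With baseline as covariate: proportional to σ²(1−ρ²).
- Large-sample ratio: (1−ρ²) / [2(1−ρ)] = (1+ρ)/2.
- Cost of estimating the slope: multiply by about 1 + 1/(N−4), where N is the total number of participants. This is 1 + 1/16 = 1.0625 at N = 20 and 1 + 1/36 = 1.028 at N = 40.

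| ρ | (1+ρ)/2 | N = 20 | N = 40 |
|---|---|---|---|
| 0.50 | 0.75 | 0.80 | 0.77 |
| 0.70 | 0.85 | 0.90 | 0.87 |
| 0.80 | 0.90 | 0.96 | 0.93 |
| 0.90 | 0.95 | 1.01 | 0.98 |
| 0.95 | 0.975 | 1.04 | 1.00 |

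A simulation (4,000 runs per setting) gave 0.90, 1.01 and 1.04 at 10 per arm for ρ = 0.7, 0.9 and 0.95. At 20 per arm it gave 0.89, 0.99 and 1.01. If the post/baseline SD ratio is 0.9 or 1.1 instead of 1, the large-sample ratio lies between 0.67 and 1.00 for ρ from 0.5 to 0.98.

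**2. Power, for illustration.** One contrast, true difference 0.8 SD of ΔCMJ, with the small-sample cost included:

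| Per arm | Unadjusted | ρ = 0.80 | ρ = 0.90 | ρ = 0.95 |
|---|---|---|---|---|
| 20 | 69.3% | 72.6% | 70.3% | 69.2% |
| 12 | 46.6% | 48.6% | 46.5% | 45.6% |

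These figures ignore the interaction gate and the correction over five contrasts.

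**3. Remainder after a chance imbalance.** Subtraction removes the whole baseline difference, whereas regression would remove ρ times it. The error left is (1−ρ) × imbalance, against the arm that started higher. For an imbalance of 0.5 SD of CMJ it is 0.25, 0.15, 0.05 and 0.025 SD of CMJ at ρ = 0.5, 0.7, 0.9 and 0.95. Dividing by √[2(1−ρ)] gives 0.25, 0.19, 0.11 and 0.08 SD of ΔCMJ. For an imbalance of one standard error of the baseline difference, the error in SDs of ΔCMJ is (1−ρ)√(2/n) / √[2(1−ρ)] = √[(1−ρ)/n], with n per arm. At n = 12 to 20 and ρ = 0.80 to 0.95 this runs from √(0.20/12) = 0.13 down to √(0.05/20) = 0.05.

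**4. Gate and T\*.** Baseline is constant over time within a participant. Group × Time contrasts computed from ΔCMJ and from raw post values agreed to about 1e-16 in the simulation. With complete data, a baseline main effect shifts all five EXP–CON differences by the same amount. The gating test and the minute with the largest difference are therefore unchanged. Only a baseline slope that varies over time could alter either.

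**The case against.** Change-score analysis is valid in a randomised comparison. It already adjusts for baseline with a fixed slope, and it is unbiased on average. If jump heights averaged over three trials are highly repeatable, ρ may be 0.9 or more. In a small trial the covariate then buys nothing and may cost a little precision. The interaction test that opens the contrasts also gains nothing from a baseline main effect. All of this stands, and it limits the size of the point.

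Four stronger readings are tempting, and the document does not support them:

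- *That chance imbalance goes uncorrected.* Each participant's baseline is subtracted; only the (1−ρ) remainder is left.
- *That the plan promises covariate-adjusted contrasts and then supplies no covariate.* The sentence ties the adjustment to Bonferroni correction, and the next section uses the word in the same sense.
- *That imbalance distorts the choice of T\*.* With a common slope all five differences move together, and nothing in the document indicates a slope that changes with time.
- *That the plan expects baseline CMJ to drive ΔCMJ.* The moderation section tests for interactions and refers to an effect of baseline, but it states no direction or size.

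What the objection does not remove is the asymmetry. At ρ = 0.5–0.7 the variance falls by 10–23% with N = 20–40, while at ρ = 0.9–0.95 the loss is at most about 4%. Nor does it explain why a variable that is already collected and already modelled is absent from the confirmatory analysis.

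**Conclusion.** The omission is real and worth mending, as an improvement in efficiency and in conditional accuracy. It is not a flaw that invalidates the comparison. It bears on the level and precision of the between-group contrasts, the difference at T* and its effect size. The precision gain is appreciable if ρ is around 0.5–0.7 and about nil or slightly negative if ρ is 0.9 or more with 10–20 per arm. Neither ρ nor N is stated, so no one can place this trial within that range from the document. The figures rest on equal SDs, 1:1 allocation, parallel arms and a two-sided 0.05 level, all assumed.

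**What to change.** Add to the primary-analysis section that mean-centred baseline CMJ, and baseline CMJ × Time, enter the Group × Time model for ΔCMJ as covariates. Take the per-minute EMM contrasts, the difference at T*, its confidence interval and its effect size from that model. Keep the unadjusted change-score model as a named sensitivity analysis. The baseline × Time term lets the slope differ by minute, and it is the only part of the change that could affect the gate or the choice of T*.

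The cost is a sentence or two of SAP text, one degree of freedom per contrast and no new data. There may be a slight loss of precision if ρ is very high and N is small. The change should be fixed before any comparison by arm is seen.
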